8.11.5.6 Monitoring and Oversight

The RBR samples will be tracked in a manner consistent with Good Clinical Practice (GCP) by a quality-controlled, auditable, and appropriately validated laboratory information management system, to ensure compliance with data confidentiality as well as adherence to authorized use of samples as specified in this protocol and in the ICF. Sponsor monitors and auditors will have direct access to appropriate parts of records relating to an individual's participation in the RBR for the purposes of verifying the data provided to the Sponsor. The site will permit monitoring, audits, IRB/EC review, and health authority inspections by providing direct access to source data and documents related to the RBR samples.

9. STATISTICAL CONSIDERATIONS

Statistical analysis will follow the estimand framework. More details on the statistical analyses will be provided in the SAP. In the event of any discrepancy between this protocol and the SAP, the SAP prevails.

9.1 STATISTICAL HYPOTHESES

The change from baseline to Year 4 in cognition, as measured by the PACC-5 score will be the primary endpoint as defined in Section 3.

The primary efficacy analysis will compare the change from baseline to Year 4 in the PACC-5 between the experimental and control arms.

The null and alternative hypotheses for the primary endpoint are as follows:

- H_0 (null hypothesis): there is no difference in the change from baseline to Year 4 in the PACC-5 between the experimental and control arms
- H_1 (alternative hypothesis): there is a difference in the change from baseline to Year 4 in the PACC-5 between the experimental and control arms

9.2 SAMPLE SIZE DETERMINATION

In this study, approximately 1200 participants will be enrolled and randomized in a 1:1 ratio to each study arm. The study is powered to compare the change from baseline to Year 4 in the PACC-5 between the experimental and control arms. Assuming a 35% dropout rate at Year 4, two-sided testing at the overall 0.05 level, a control arm coefficient of variation (CV) of 1.99 for the Year 4 change scores (=standard deviation of control participant change scores/mean of control participant change scores) and 600 participants per arm, the study will have at least 80% power to detect a true effect of 40% reduction of the mean PACC-5 decline in the control arm.

The assumption for the control arm CV is based on data from a population with similar inclusion and exclusion criteria in 4 observational cohorts (ADNI, AIBL; Biomarkers for Identifying Neurodegenerative Disorders Early and Reliably Study [BioFINDER], HABS).

An increase in sample size and/or duration of the study may be considered if factors external to the study or blinded study data analysis warrant a change to the sample size assumption. As a result, the sample size may be increased from 1200 up to 1800 participants (900 participants per arm). Further details will be described in the SAP. The assessment will be performed by the Sponsor at a specified timepoint. The Sponsor will remain blinded and the sample size will not be reduced on the basis of this assessment.

The planned number of participants who take part in the optional longitudinal amyloid PET assessment is approximately 400 participants (200 participants per study arm). The planned number of participants was selected primarily based on practical feasibility.

The planned number of participants who take part in the optional longitudinal tau PET assessment is approximately 600 participants (300 participants per study arm). The planned number of participants was selected primarily based on practical feasibility. Subject to operational feasibility, this number may be increased to a maximum of 800 participants (400 participants per study arm).

The planned number of participants who take part in the optional longitudinal CSF assessment is approximately 400 participants (200 participants per study arm). The planned number of participants was selected primarily based on practical feasibility and not based on power calculations.

9.3 ANALYSIS SETS

The analysis sets are defined in [Table 10](#).

Table 10 Analysis Sets and Description

Participant Analysis Set	Description
All Randomized Participants	All participants randomly assigned to study treatment
Safety	All participants randomly assigned to study treatment and who receive at least 1 dose of study drug

All analyses will be performed on the all randomized participant population, unless specified otherwise.

All safety analyses will be performed on the safety population and participants will be grouped according to the treatment they actually received. For all efficacy analyses, participants will be grouped according to the treatment assigned at randomization.

9.4 STATISTICAL ANALYSES

The SAP will be finalized prior to the locking and unblinding of the study database, and it will include a more technical and detailed description of the statistical analyses described in this section.

In particular, supplementary estimands and details concerning the estimand strategy will be defined in the SAP, as well as any sensitivity analyses to the estimands of study endpoints, and any pre-specified subgroup analyses.

The following sections present the planned statistical analyses of the most important endpoints, including the primary endpoint.

9.4.1 General Considerations

In addition to the analyses detailed in the following sections, study results will be presented by study arm (with total when appropriate) and summarized according to the type of the variables:

- For continuous variables, using descriptive statistics such as the mean, standard deviation, median, and range, as appropriate, including the number of participants contributing to these statistics
- For categorical variables, using the frequency and proportion of participants falling into each category, grouped by study arm (and total). The percentages reported in these tables will be rounded; therefore, may not always sum to 100%.

The type I error will be controlled at a 2-sided 0.05 level for multiplicity across the primary and confirmatory secondary endpoints. The confirmatory secondary endpoints, a subset of the secondary endpoints described in Section 3, will be specified in the SAP.

9.4.2 Primary Endpoint

9.4.2.1 Primary Estimand

The change from baseline to Year 4 in cognition, as measured by the PACC-5 score is the primary endpoint.

If a participant withdraws from study treatment, the reason for withdrawal will be classified as either study drug or condition-related (SDCR) or not study drug or condition-related (NSDCR). More details of this classification will be given in the SAP.

The primary comparison of interest is the difference between the experimental and control arms in the change from baseline to Year 4 in cognition, as measured by the PACC-5 score. The primary comparison will be made regardless of whether:

- A participant initiates a symptomatic treatment for AD (e.g., acetylcholinesterase inhibitors and memantine) after progression to dementia due to AD as determined by the iCAC
- A participant has a treatment interruption due to ARIA-E or safety reasons (e.g., short-term anticoagulation)
- A participant withdraws from the study treatment due to a SDCR reason

Further, the primary comparison will be made in the hypothetical scenario that a NSDCR withdrawal from the study treatment would not have occurred.

Note that the control arm will contain both participants who do not meet the clinical progression criteria and remain on placebo throughout the duration of the study and participants who meet the clinical progression criteria and initiate active gantenerumab at the time of the clinical progression.

The elements of the primary estimand as per the estimand framework introduced in the ICH-E9 (R1) addendum (ICH 2019) as well as the intercurrent events and the handling strategies are defined in [Table 11](#). A full list of intercurrent events will be specified in the SAP.

Table 11 Primary Estimand and Estimand Framework

Primary Estimand	Estimand Framework
Population	Participants at risk for or at the earliest stages of AD as defined by the study inclusion and exclusion criteria
Primary efficacy variable	Change from baseline to Year 4 in the PACC-5
Treatment	Gantenerumab treatment with a target dose of 255 mg Q1W or 510 mg Q2W versus placebo followed by gantenerumab upon the diagnosis of MCI or dementia due to AD by the iCAC
Summary measure	The difference in variable means between study arms
Intercurrent events	
 • SDCR withdrawal from study treatment: a treatment policy strategy will be applied • NSDCR withdrawal from study treatment: a hypothetical strategy will be applied • Treatment interruption due to ARIA-E or safety reasons: a treatment policy strategy will be applied • Initiation of symptomatic treatment for AD (e.g., acetylcholinesterase inhibitors and memantine) after progression to dementia due to AD as determined by the iCAC: a treatment policy strategy will be applied 
A full list of intercurrent events will be specified in the SAP.

AD=Alzheimer’s disease; ARIA-E=amyloid-related imaging abnormalities–edema/effusion; iCAC=independent Clinical Adjudication Committee; MCI=mild cognitive impairment; NSDCR=not study drug or condition-related; PACC-5=Preclinical Alzheimer’s Cognitive Composite-5; Q1W=every 1 week; Q2W=every 2 weeks; SAP=Statistical Analysis Plan; SDCR=study drug or condition-related.

9.4.2.2 Primary Estimator

The difference in mean change from baseline to Year 4 in the PACC-5 will be estimated with use of a longitudinal data model adjusting for the randomization stratification factors. Formal statistical testing of the difference between the two arms will be performed for the Year 4 visit. When applying the treatment policy strategy, all the available data will be included in the analysis. When applying the hypothetical strategy, data will be censored at the time of the intercurrent events (i.e., NSDCR withdrawal from study treatment) and data after the intercurrent events will be imputed. The imputation rules will be described in the SAP.

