ADA = anti-drug antibody; AD-CGI-S = Clinician Global Impression of Cognitive Function; AD-PGI-S = Participant Global Impression of Cognitive Function; AD-SPGI-S = Study Partner Global Impression of Cognitive Function; A-IADL-Q-SV = Amsterdam Instrumental Activities of Daily Living Questionnaire Short Version; APOE = apolipoprotein E; ARIA-E = amyloid-related imaging abnormalities – edema/effusion; ARIA-H = amyloid-related imaging abnormalities – hemosiderin deposition; BBBM = blood-based biomarker; C = in-clinic administration by study staff; CDR = Clinical Dementia Rating; CF_{1a} = Cognitive Function Instrument acute; CRP = C-reactive protein; C-SSRS = Columbia-Suicide Severity Rating Scale; CS = supervised in-clinic administration, where applicable; CSF = cerebrospinal fluid; DCF = Diagnostic Classification Form; Early Term = Early Termination; EQ-5D-5L = EuroQol 5-Dimension 5-Level Questionnaire; GDS-30 = Geriatric Depression Scale; H = visit appropriate for home administration by participant or study partner, where applicable; HBV = hepatitis B virus; HCV = hepatitis C virus; CF = Informed Consent Form; Max. = maximum; *MN* = *visit appropriate for home administration by mobile nursing professional, where applicable*; MRI = magnetic resonance imaging; PACC-5 = Preclinical Alzheimer's Cognitive Composite-5; PET = positron emission tomography; PK = pharmacokinetic; Q1W = every 1 week; RBANS = Repeatable Battery for the Assessment of Neuropsychological Status; Unsch = unscheduled; Wk = week.

x^B = before study drug administration; visits may be split over 2 consecutive days.

The baseline visit (Week 1) may be split over 5 consecutive business days. All cognitive and functional assessments must be completed first, and before study drug administration. All safety assessments (e.g., vitals, blood tests, and ECGs) must be completed on the day of dosing and before study drug administration. Study drug administration should be the last baseline visit activity, marking the end of Week 1.

Participants should be observed for at least 2 hours after dosing for the first 4 administrations of study drug (corresponding to the injections at Week 1, Week 5, Week 9 and Week 13); the observation time may be reduced to at least 1 hour following all other administrations.

- a Not applicable for sites where BBBM prescreening is not approved. Participation in the optional BBBM prescreening requires signing of the separate BBBM prescreening ICF.

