6.3 TREATMENT ASSIGNMENT AND BLINDING

6.3.1 Treatment Assignment

This is a randomized, double-blind study. After the main study written informed consent has been obtained, all screening procedures and assessments have been completed, and eligibility has been established for a participant, the study site will obtain the participant's identification number and treatment kit assignment from an IxRS. Participants will be randomly assigned to 1 of 2 treatment arms. The ratio will be 1:1, 1 experimental to 1 control. The randomization method will be stratified block-randomization. Randomization to treatment allocation will be stratified by the following criteria: geographic region (Western Europe, Australia, and New Zealand), the participant's *APOE* ϵ 4 carrier status (non-carrier vs. heterozygote carrier vs. homozygote carrier), the method used to determine amyloid positivity (PET vs. CSF), and participation in the optional longitudinal amyloid PET and tau PET assessments.

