9.4.3 Secondary Endpoints

The secondary endpoints are described in Section 3. The confirmatory secondary endpoints, a subset of the secondary endpoints described in Section 3, will be specified in the SAP.

A multiple testing procedure will be applied to adjust for multiple statistical testing of the confirmatory secondary endpoints. The overall type I error rate will thereby be controlled. Details about the multiple statistical testing procedure will be given in the SAP.

The remaining secondary endpoints will not be adjusted for multiple testing.

The following continuous secondary efficacy endpoints will be analyzed in the same way as the primary efficacy endpoint:

- Change from baseline to Year 4 in cognitive functional activities of daily living, as measured by the CFIA and the A-IADL-Q-SV
- Change from baseline to Year 4 in cognition and function, as measured by the CDR-SB

The following time to event secondary efficacy endpoints will be analyzed with use of an estimand whose elements, as per the estimand framework introduced in the ICH-E9 (R1) addendum (ICH 2019), will be described in the SAP:

- Time to onset of confirmed clinical progression, defined as the time from randomization to the first occurrence of 2 consecutive visits (approximately 6 months apart) with a CDR-GS > 0
- Time from randomization to clinical progression to MCI or dementia due to AD based on the diagnosis of the independent Clinical Adjudication Committee (iCAC)

The comparison of interest is between the experimental and control arms.

The appropriate statistical methods for time to event secondary efficacy endpoints will be described in the SAP and could include, for example, Cox proportional hazards regression.

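### The primary model for PACC-5 change names only the stratification factors as covariates; stating that baseline PACC-5 also enters would be a nearly free gain in precision

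*Combined protocol and SAP*

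**What the plan says.** Section 9.4.2.2 says the difference in mean change from baseline to Year 4 will be estimated with "a longitudinal data model adjusting for the randomization stratification factors". No other covariate is named.

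Section 6.3.1 ("Randomization to treatment allocation will be stratified by the following criteria") gives the factors: geographic region, APOE ε4 carrier status, PET or CSF as the method of establishing amyloid positivity, and participation in the optional longitudinal PET assessments.

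Elsewhere in Section 9, baseline PACC-5 appears only as the reference point of the change score. Section 9.4.5.2 defines a baseline value (the last one before treatment starts), but for descriptive summaries.

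Tables 1 and 4 schedule PACC-5 at screening and at the baseline visit, where "All cognitive and functional assessments must be completed first, and before study drug administration". The population summary in Table 11 is "The difference in variable means between study arms".

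Section 9.4.3 extends the model to CFIa, A-IADL-Q-SV and CDR-SB: "The following continuous secondary efficacy endpoints will be analyzed in the same way as the primary efficacy endpoint".

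Section 9.4 says of the SAP that "it will include a more technical and detailed description of the statistical analyses described in this section", and Section 9 says the SAP prevails over the protocol. The document contains no SAP text.

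**The concern.** When the outcome is a change from baseline, the baseline score of the same instrument is the obvious covariate to consider. The plan lists an adjustment set for its primary test and leaves that score out. An analyst who fitted the model as written would discard whatever precision baseline PACC-5 carries.

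The sample size leaves no slack to absorb that loss. Section 9.2 claims "the study will have at least 80% power to detect a true effect of 40% reduction", and the calculation behind the claim uses the coefficient of variation of raw Year 4 change scores with no mention of baseline adjustment.

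Adjustment would also deal with chance imbalance between arms in baseline cognition. That is the same benefit as the precision gain and should not be counted twice.

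**Working it through.** **Inputs from Section 9.2.** 600 per arm, 35% dropout at Year 4, control-arm CV 1.99 for Year 4 change, a 40% reduction of the mean control decline, two-sided 0.05.

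**Reproducing the stated power.**
- Completers per arm: 600 × 0.65 = 390.
- Standardised effect: 0.40 / 1.99 = 0.2010.
- Noncentrality: 0.2010 × √(390/2) = 2.807.
- Power: 80.15% (normal) or 80.05% (t). This agrees with the plan.
- Smallest size for 80%: 389 completers, and 389 / 0.65 rounds up to 599 randomised per arm, against 600 planned.

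**Adding baseline.** If r is the correlation between baseline PACC-5 and Year 4 change, the residual SD becomes 1.99 × √(1 − r²). The documents do not give r, so these values are assumptions:

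| Absolute r | Variance ratio 1 − r² | Power, 390 completers | Completers per arm for 80% | Randomised per arm for 80% | Power, 585 completers |
|---|---|---|---|---|---|
| 0 | 1.00 | 80.1% | 389 | 599 | 93.0% |
| 0.2 | 0.96 | 81.7% | 373 | 574 | 93.9% |
| 0.3 | 0.91 | 83.7% | 354 | 545 | 95.0% |
| 0.4 | 0.84 | 86.5% | 327 | 504 | 96.3% |

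The last column covers the blinded option in Section 9.2 under which "the sample size may be increased from 1200 up to 1800 participants (900 participants per arm"): 900 × 0.65 = 585 completers.

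**Cost if baseline carries nothing.** With r = 0 the variance is inflated by about 1 + 1/776 = 1.0013 (776 = 780 completers − 4). Power is 80.10% instead of 80.15%. Break-even is an absolute r of about 0.036.

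**Can the documents narrow r?** Section 4.2.1 gives a PACC-5 decline of 0.14 to 0.26 SD per year. Assume that these are baseline SDs, that decline is linear over 4 years, and that the CV of 1.99 applies. In baseline SDs, the SD of change is then s = 1.99 × 4 × rate, which is 1.11 or 2.07. For an assumed baseline to Year 4 correlation R, the Year 4 SD is k = R + √(R² − 1 + s²), and r = (Rk − 1)/s.

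| Decline per year | R | Variance saved (r²) | Power, 390 completers |
|---|---|---|---|
| 0.14 SD | 0.6 | 2.5% | 81.1% |
| 0.14 SD | 0.7 | 0.6% | 80.4% |
| 0.14 SD | 0.8 | 12.3% | 85.0% |
| 0.26 SD | 0.4 | 0.2% | 80.2% |
| 0.26 SD | 0.5 | 0.8% | 80.5% |
| 0.26 SD | 0.6 | 6.0% | 82.5% |
| 0.26 SD | 0.7 | 16.9% | 86.8% |
| 0.26 SD | 0.8 | 35.0% | 93.6% |

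The gain runs from negligible to large, so the documents do not fix it.

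**The case against.** The strongest reply is that Section 9.4.2.2 is a summary. It does not say that the stratification factors are the only terms, and it also omits visit, treatment by visit and the covariance structure, which any such model would need. The covariate list is the sort of detail deferred to a SAP that overrides the protocol. The generic model description is also compatible with having baseline in the response vector. All of this stands, and it is why the point is an improvement to make or confirm and not an error. But the section does choose to name an adjustment set, and a literal reading leaves baseline out.

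Three points about size also stand.
- The table compares an unadjusted completer analysis with adjustment for baseline alone. The planned model already uses the stratification factors, so the true increment depends on the correlation of baseline with change given those factors and the other visits.
- Entry requires CDR-GS 0 and RBANS DMI of at least 80, which may narrow the spread of baseline PACC-5, CFIa and A-IADL-Q-SV.
- Below an absolute correlation of about 0.036, precision falls very slightly.

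None of these changes the direction of the argument or makes the fix costly.

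**Conclusion.** The point holds. As written, the primary model names no baseline cognitive score, and no other text supplies one. The analysis is valid and the stated power reproduces; what may be lost is precision.

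At 600 per arm the gain is about 1.6, 3.6 or 6.3 percentage points of power for an absolute baseline–change correlation of 0.2, 0.3 or 0.4. It may be close to zero. At 900 per arm the corresponding gains are about 0.9, 2.0 and 3.3 points.

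These figures assume a completer comparison at Year 4 with the CV of 1.99. They do not count the stratification factors, the intermediate visits or the partial data from dropouts that a longitudinal model would use. The worst-case cost is about 0.05 points, so the change is worth making even though its benefit is unknown.

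**What to change.** In Section 9.4.2.2 and in the SAP, add baseline PACC-5 (the last pre-dose value, as defined in Section 9.4.5.2) and its interaction with visit beside the stratification factors. Alternatively, specify a constrained longitudinal model with baseline in the response vector and a common baseline mean across arms. If the SAP already does either, aligning the protocol sentence is enough.

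Apply the same rule to CFIa and A-IADL-Q-SV, each with its own baseline. Apply it to CDR-SB for consistency only: entry at CDR-GS 0 leaves little baseline variation to exploit.

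The cost is one sentence in each document and about one degree of freedom per added term. No new data are needed and the estimand in Table 11 is unchanged. The choice should be fixed before unblinding.

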9.4.3 Secondary Endpoints

The secondary endpoints are described in Section 3. The confirmatory secondary endpoints, a subset of the secondary endpoints described in Section 3, will be specified in the SAP.

A multiple testing procedure will be applied to adjust for multiple statistical testing of the confirmatory secondary endpoints. The overall type I error rate will thereby be controlled. Details about the multiple statistical testing procedure will be given in the SAP.

The remaining secondary endpoints will not be adjusted for multiple testing.

The following continuous secondary efficacy endpoints will be analyzed in the same way as the primary efficacy endpoint:

- Change from baseline to Year 4 in cognitive functional activities of daily living, as measured by the CFIA and the A-IADL-Q-SV
- Change from baseline to Year 4 in cognition and function, as measured by the CDR-SB

The following time to event secondary efficacy endpoints will be analyzed with use of an estimand whose elements, as per the estimand framework introduced in the ICH-E9 (R1) addendum (ICH 2019), will be described in the SAP:

- Time to onset of confirmed clinical progression, defined as the time from randomization to the first occurrence of 2 consecutive visits (approximately 6 months apart) with a CDR-GS > 0
- Time from randomization to clinical progression to MCI or dementia due to AD based on the diagnosis of the independent Clinical Adjudication Committee (iCAC)

The comparison of interest is between the experimental and control arms.

The appropriate statistical methods for time to event secondary efficacy endpoints will be described in the SAP and could include, for example, Cox proportional hazards regression.

